2.3. Benefit/Risk Assessment

PF-07923568 is not expected to provide any clinical benefit to healthy participants. This study is designed primarily to generate safety, tolerability, and PK data for further clinical development.

For healthy participants participating in this study, no clinical benefit is expected. The purpose of the study is to provide the basis for further clinical development of PF-07923568 as a potential new, pharmacological agent for the treatment of RSV. As of 14 September 2022, no specific human risks have been identified; postulated risks based on nonclinical studies are summarized in [Section 2.2.3](#). The clinical impact of these potential risks will be minimized through standard, intensive, inpatient monitoring of the participants following administration of multiple oral doses of the study intervention.

More detailed information about the known and expected benefits and risks and reasonably expected AEs of sisunatovir may be found in the IB, which is the SRSD for this study.

2.3.1. Risk Assessment

| Potential Risk of Clinical Significance | Summary of Data/Rationale for Risk | Mitigation Strategy |
|---|--|---|
| Study Intervention PF-07923568 | | |
| Hepatobiliary system effects | Degenerative and inflammatory changes in the bile duct of both rats (≥ 60 mg/kg/day) and dogs (≥ 45 mg/kg/day) in studies of up to 28 days, with elevated plasma levels of ALP, ALT, and GGT in dogs only. Evidence of recovery for all findings following a 14-day treatment-free period. | Standard monitoring including laboratory (ie, transaminases, ALP, GGT) and AE monitoring. |

| Potential Risk of Clinical Significance | Summary of Data/Rationale for Risk | Mitigation Strategy |
|---|---|---|
| Gastrointestinal effects | 
Transient dose-related incidence of emesis and liquid feces in dogs at doses ≥ 15 mg/kg/day in studies up to 28 days. Additionally, inflammation in the duodenum, gall bladder, and liver at 45 mg/kg/day noted in 28-day dog study.
 
In previous clinical studies sisunatovir has been associated with mild GI AEs in fasted state.
 | As this is an investigational agent, there is some risk that is mitigated by close observation of AEs, etc. Participants will be closely evaluated in an inpatient setting to monitor for GI AEs. If needed, palliative alleviating measures such as antiemetics may be provided. |
| Renal effects | Degeneration/regeneration of medullary tubules was noted in rats at ≥ 120 mg/kg/day in studies of up to 28 days; considered non-adverse based on lack of clinical pathology changes. | Standard monitoring including laboratory and AE monitoring. |
| Cardiovascular effects | 
Myocardial degeneration and necrosis were noted at 240 mg/kg/day (non-tolerated dose) in a 14-day rat study.
 
No similar effect in rats at 120 mg/kg/day in the 28-day study, or in dogs at any dose, for 14 or 28 days.
 
Phase 1 first-in-human (FIH) study (C5241001) showed no adverse clinically significant changes in safety laboratory parameters (including troponin), ECGs, and VS.
 | Monitoring will include VS, including heart rate and ECG assessments. |
| Pulmonary effects | 
Vascular degeneration/necrosis in lung at 240 mg/kg/day and epithelial degeneration/necrosis in trachea at 120 mg/kg/day in 14-day rat study.
 
No similar effect in rats at 120 mg/kg/day in the 28-day study, or in dogs at any dose, for 14 or 28 days.
 
Phase 1 FIH study (C5241001) showed no adverse clinically significant changes in safety laboratory parameters (including troponin), ECGs, and VS.
 | There will be standard safety monitoring including VS and AEs. |
| Thymus effects | 
Lymphoid atrophy and decreased thymus weight and reduced size of thymus in both rats (≥ 120 mg/kg/day) and dogs ≥ 15 mg/kg/day) in studies of up to 28 days.
 
Evidence of recovery following a 14-day treatment-free period.
 
These findings are secondary to stress and not directly sisunatovir-related.
 | Standard monitoring including laboratory (ie, complete blood count with differential) and AE monitoring. Single dose regimen should further limit this potential risk. |
| Other | | |
| Risk of COVID-19 exposure during study | During the pandemic, study participants could be exposed to the SARS-CoV-2 virus during study participation. This could lead to increased health risk for this participant and others in the study. | Assessment of risk for, symptoms of, or testing for COVID-19 may be performed at screening, admission to the CRU, and/or at other times during the study at investigator discretion and according to local site policies. |

2.3.2. Benefit Assessment

A single dose of PF-07923568 is not expected to provide any clinical benefit to study participants. This study is designed primarily to characterize the effect of varying degrees of hepatic impairment on the PK of PF-07923568 to support further clinical development of PF-07923568 as a potential treatment of RSV. Results from this study will be used in conjunction with collective safety, tolerability, efficacy, and PK/PD data from other PF-07923568 studies to develop dosing recommendations for the target patient population with varying degrees of hepatic function.

2.3.3. Overall Benefit/Risk Conclusion

PF-07923568 is not expected to provide any clinical benefit to healthy participants in this study.

Based on the profile of PF-07923568 observed in nonclinical and clinical studies to date, and taking into account the measures to minimize risk to study participants, the potential risk to the participants in this study is deemed to be minimal and is justified by the anticipated benefits that may be afforded to patients with varying degrees of HI receiving PF-07923568 in the future.

3. OBJECTIVES AND ENDPOINTS

| Objectives | Endpoints |
|---|--|
| Primary: | Primary: |
| 
To compare the PK of PF-07923568 following administration of a single oral dose in adult participants with varying degrees of HI relative to age- and body weight-matched participants without HI. | 
Plasma: C_{max}, AUC_{last} or AUC_{inf}^*, as data permit. |
| Secondary: | Secondary: |
| 
To evaluate the safety and tolerability of a single oral dose of PF-07923568 when administered to adult participants with varying degrees of HI and in age- and body weight-matched participants without HI. | 
Assessment of TEAEs, clinical laboratory abnormalities, VS, ECG parameters. |
| Tertiary/Exploratory: | Tertiary/Exploratory: |
| 
To compare additional PK parameters of PF-07923568 following administration of a single oral dose in adult participants with varying degrees of HI and in age- and body weight-matched participants without HI. | 
Plasma: CL/F, V_z/F, T_{max} and $t_{1/2}$ as data permit. |

* AUC_{last} will be treated as primary endpoints if data do not permit robust estimation of AUC_{inf} , otherwise they will be treated as tertiary endpoints.

4. STUDY DESIGN

4.1. Overall Design

This is an open-label, single-dose, parallel-group, multicenter study to investigate the effect of varying degrees of hepatic function on the plasma PK of PF-07923568 after a single, oral **CCI** mg dose administered in the fed state (standard breakfast). Safety and tolerability will be evaluated throughout the study. A total of approximately 28-32 participants with varying degrees of hepatic function will be administered as a single, oral **CCI** mg dose of PF-07923568 in the fed state as shown in Table 3.

Table 3. Hepatic Function Categories Based on Child-Pugh Score

| Group | Description | Child-Pugh Score | Number of Participants |
|-------|-------------|---------------------------|------------------------|
| 1 | Without HI | Not Applicable | 8 ^a |
| 2 | Mild HI | Class A (5 to 6 points) | 8 |
| 3 | Moderate HI | Class B (7 to 9 points) | 8 |
| 4 | Severe HI | Class C (10 to 15 points) | 4-8 ^b |

a. Additional participants may be dosed to a maximum of 10 participants to ensure mean age ± 10 years and mean body weight ± 15 kg of this group is aligned with the pooled average assessed when approximately $\geq 75\%$ of participants are dosed across the other 3 groups.

b. The total number of participants enrolled that are classified as having severe HI will be a minimum of 4 to a maximum of 8 depending on recruitment rates.

Categorization of participants into Groups 2-4 will be done based on Child-Pugh scores determined, as described in [Appendix 10](#) at the screening visit.

Staged Enrollment of Study Groups

[figure not shown]
Participants will be dosed in a staged manner as follows:

- Participants with moderate HI (Group 3) and severe HI (Group 4) will be enrolled first.
- Recruitment of participants with mild HI (Group 2) will initiate when approximately 50% of the participants in Group 3 have been dosed.
- Sponsor approval is required before proceeding with recruitment of Group 2.*
- An average value for age and weight for the 3 HI groups (Groups 2-4) will be determined and participants without HI (Group 1) will be recruited to match the average demographics (at a minimum, age and weight, and as much as practically possible gender) across the pooled Groups 2-4.

- Recruitment for healthy participants in Group 1 (without HI) may start when approximately 75% of total participants across Groups 2-4 (ie, approximately 15 to 18 participants) have been dosed.
- ***Sponsor approval is required before proceeding with recruitment of Group 1.***

Participants who prematurely discontinue before completing all assessments may be replaced, at the discretion of the investigator and sponsor study team.

The overall study design is presented as a schematic in [Section 1.2](#) and below. For individual participants, the total duration of participation from the screening visit to the follow-up visit will range from approximately 5 weeks (minimum) to approximately 8 weeks (maximum). The study consists of an initial screening period of up to 28 days (while allowing for the return and review of all results, including laboratory tests), a 6-day inpatient stay at the CRU which includes administration of a single oral dose of PF-07923568, and a follow-up contact that will occur 28-35 days after PF-07923568 administration.

- a. Admission can occur at any time of day; once admitted, participant to be provided inpatient meal(s).
- b. Following completion of procedures and morning meal, participant will be discharged from the CRU.
- c. Follow-up telephone contact may occur as onsite visit for follow-up of abnormal laboratory tests and/or open AEs, at Investigator discretion, in the window of 28 to 35 days after Day 1.

4.2. Scientific Rationale for Study Design

The purpose of this study is to characterize the effect of varying degrees of HI on the PK, safety and tolerability of PF-07923568. A single dose of PF-07923568 is proposed, as single dose plasma PK of PF-07923568 is generally predictive of exposure upon repeated dosing. Mean predicted accumulation index for a single dose of 175-350 mg comparable to the mean observed accumulation after multiple doses of 175-350 mg BID for 5 days.

There is uncertainty of the effect of HI on PF-07923568 PK. *In vitro* and *in vivo* studies indicate that PF-07923568 is predominantly eliminated through hepatic metabolism. CYP3A4 is the main CYP isoform that metabolizes PF-07923568 with minor contribution from CYPs 2C9 and 2D6. Based on review of the effect of hepatic impairment on human PK for compounds cleared in a similar manner to PF-07923568 (CYP3A-mediated metabolism), impaired hepatic function is generally associated with increased drug exposures in plasma (internal data and data cited in University of Washington Drug Interaction Database).

However, the magnitude of this increase in exposure is variable between compounds with some being only modestly impacted, while others exhibit increases in exposure even greater than 2-fold when participants with severe hepatic impairment are considered. As such, this study will enroll participants with varying degrees of hepatic impairment, and participants without hepatic impairment (matched for age as well as body weight and gender, as much as practically possible) in order to allow a robust assessment of PK across the entire spectrum of hepatic function.

Nonclinical studies indicate that the clearance of sisunatovir following oral administration to rats is predominantly hepatic. A rat bile-duct cannulated study showed negligible renal excretion (Study PPN70-058.04). Furthermore, an ADME (absorption, distribution, metabolism, and excretion) study in male Sprague-Dawley rats that received a single oral administration of [¹⁴C]-sisunatovir showed that excretion was predominantly via the fecal route and urine accounted for <4% of the dose (Study RVL/01). It is anticipated that renal excretion will be similarly low in humans.

Given the elimination of sisunatovir via hepatic enzymes with minimal contribution by renal elimination, it is expected that HI could have an effect on the clearance of sisunatovir. Following administration of single doses of PF-07923568, the arithmetic mean terminal t_{1/2} of PF-07923568 ranged from 7-10 hours. Even with a possible modest increase in half-life, serial PK samples will be collected over 120 hours post-dose, which is expected to adequately characterize the elimination phase of the plasma concentration-time profile in the cohorts with varying degrees of HI. The protein binding of PF-07923568 in humans is 33%, resulting in a high fu of 67%.

Available PK data with PF-07923568 administered under fasted or fed conditions indicate that PF-07923568 may be administered without regard to food. Overall, administration of PF-07923568 with food results in a slight reduction in observed variability and trended towards having fewer GI TEAEs. In this study, a single dose of CCI mg PF-07923568 will be administered with a standard breakfast to reflect the conditions for anticipated use of PF-07923568 in future trials.

In general, participants with normal hepatic function (Group 1) will abstain from concomitant treatments, except for the treatment of AEs. Use of selected limited prescription and non-prescription medications may be permitted (refer to [Section 6.9](#) for details). Participants with impaired hepatic function (Groups 2-4) are permitted to be on stable doses of background medications for the management of their concomitant medical condition(s) with some exclusions (see [Appendix 9](#)). According to the DDI risk assessment for PF-07923568 as described in [Section 2.2.2](#), sisunatovir is a moderate inhibitor of CYP3A4 and is projected to be a weak inhibitor of CYP2B6. For this reason sensitive and narrow TI CYP3A4 substrates and sensitive narrow TI CYP2B6 substrates are prohibited in this study. Since PF-07923568 is a P-gp and CYP3A4 substrate, strong and moderate CYP3A4 inhibitors and strong P-gp inhibitors are also prohibited. Lastly, due to risk of MATE1 and OCT1 inhibition, sensitive substrates of these transporters are prohibited.

To minimize the risks of COVID-19 related complications to participants and the study site personnel, assessment of risk for, symptoms of or testing for COVID-19 may be performed at screening, admission to the CRU, and/or at other times during the study at investigator discretion and according to local site policies.

The Child-Pugh Classification (refer to [Appendix 10](#)) will be used to define the 3 groups of participants with varying degrees of HI. This study will include participants with mild (Child-Pugh Class A, Group 2), moderate (Child-Pugh Class B, Group 3), and severe (Child-Pugh Class C, Group 4) HI as well as demographically matched control participants without HI (Group 1). All participants will be required to provide their own consent to participate in this study, hence participants with clinically active Grade 3 or Grade 4 encephalopathy will be excluded. However, participants who have a previous history of Grade 3 or 4 encephalopathy but are currently receiving an intervention (eg, lactulose or lactitol, alone or in combination with rifaximin, and/or neomycin) to manage their encephalopathy-related signs and symptoms are eligible provided the on-treatment encephalopathy grading at the screening visit is Grade 2 or lower, thereby permitting them to provide their own informed consent. Acknowledging the medical state of the population enrolled, certain eligibility criteria for participants with hepatic impairment are distinctly different, with no specific exclusion of participants with Hepatitis B and Hepatitis C in Groups 2-4.

4.2.1. Choice of Contraception/Barrier Requirements

Human reproductive safety data are limited for sisunatovir, but there is no suspicion of human teratogenicity based on the intended pharmacology of the compound. Therefore the use of a highly effective method of contraception is required for all fertile participants (see [Appendix 4](#)).

4.2.2. Collection of Retained Research Samples

Retained Research Samples will be collected and stored for further analyses which may, for example, provide greater understanding of the study intervention.

4.3. Justification for Dose

While there is uncertainty of the effects of HI on the exposure of PF-07923568 and the metabolism by CYP3A4, the proposed dose of [CCI](#) mg is expected to be safe and well-tolerated in participants with HI.

This dose has been selected based on prior experience in clinical studies with PF-07923568 ([Section 2.2.4](#)) demonstrating that it is safe and well tolerated. The clinical program for PF-07923568 has evaluated doses up to 350 mg twice daily (BID) for 5 days to date.

The clinical program for PF-07923568 has evaluated doses up to 350 mg twice daily (BID) for 5 days to date. PF-07923568 was generally well tolerated in the viral challenge study (C5241002) as well as other Phase 1 studies conducted to date. However, under fasting conditions an increased incidence of GI AEs, primarily mild and moderate HI, were observed.

at the 350 mg dose relative to the 200 mg dose. Higher rates of GI AEs were also observed at higher doses within the Phase 1 program. In these studies, sisunatovir was dosed in a fasted state. Although improved GI tolerability has been observed for some anti-infective agents when dosed with food, it is not clear if GI tolerability of sisunatovir will improve with food. The effect of food on the PK of sisunatovir has been variable in Phase 1 studies. However, the effect of food on the PK of sisunatovir using the formulation to be used in this study (DPB in capsules) showed minimal food effect accompanied by a decrease in observed variability. Given the above, it is anticipated that with a single **CCI** mg dose potential increases in plasma exposure in participants with varying degrees of hepatic impairment in the current study, if encountered, are not anticipated to pose an undue safety risk.

4.4. End of Study Definition

The end of the study is defined as the date of the follow-up as shown in the [SoA](#) for the last participant in the trial globally.

A participant is considered to have completed the study if they have completed all phases of the study, including the follow-up visit (telephone contact or onsite visit per investigator discretion) as shown in the [SoA](#).

5. STUDY POPULATION

This study can fulfill its objectives only if appropriate participants are enrolled, including participants across diverse and representative racial and ethnic backgrounds. Use of a prescreening tool is utilized for study recruitment purposes, it will include collection of information that reflects the enrollment of a diverse participant population including, where permitted under local regulations, age, sex, and race, and ethnicity. The following eligibility criteria are designed to select participants for whom participation in the study is considered appropriate. All relevant medical and nonmedical conditions should be taken into consideration when deciding whether a particular participant is suitable for this protocol.

Prospective approval of protocol deviations to recruitment and enrollment criteria, also known as protocol waivers or exemptions, is not permitted.

5.1. Inclusion Criteria

Participants are eligible to be included in the study only if all of the following criteria apply:

5.1.1. Participants in All Groups

Age and Sex:

1. Male or female between the ages of 18 (or the minimum country-specific age of consent if >18) and 75 years, inclusive, at the screening visit.

WOCBP, however, cannot be pregnant, breastfeeding, or planning to become pregnant while participating in the study. Refer to [Appendix 4](#) for reproductive criteria for male ([Section 10.4.1](#)) and female ([Section 10.4.2](#)) participants.

Other Inclusion Criteria:

2. Willing and able to comply with all scheduled visits, treatment plan, laboratory tests, lifestyle considerations (as described in [Section 5.3](#)), and other study procedures.
3. BMI of 17.5 to 38.0 kg/m², inclusive; and a total body weight >50 kg (110 lb), at the screening visit; with a single repeat assessment of total body weight (and hence BMI), on a separate day before Day -1 permitted to assess eligibility, if needed.
4. Capable of giving signed informed consent as described in [Appendix 1](#), which includes compliance with the requirements and restrictions listed in the ICD and in this protocol.

5.1.2. Additional Inclusion Criteria for Group 1 *Only* (without HI)

1. At screening, no clinically relevant abnormalities identified by a detailed medical history, complete PE, including BP and pulse rate measurement, 12-lead ECG and clinical laboratory tests, as assessed by the sponsor approved laboratory.
2. At screening, participants must meet the demographic-matching criteria, including:
 - A body weight that is within ± 15 kg of the average of the pooled hepatic impairment groups (Groups 2-4), as provided by the sponsor;
 - An age that is within ± 10 years of the average of the pooled hepatic impairment groups (Groups 2-4), as provided by the sponsor;
 - *Attempts will be made* to ensure that the male-to-female distribution in Group 1 is comparable to that in the pooled hepatic impairment groups (Groups 2-4).
3. No known or suspected hepatic impairment, and meet all the following criteria at screening, as assessed by the sponsor approved laboratory, with a single repeat permitted to assess eligibility, if needed:
 - ALT \leq ULN;
 - AST \leq ULN;
 - T bili \leq ULN.

NOTE: Participants with a history of Gilbert syndrome (and hence elevated T bili) are eligible provided direct bilirubin level is \leq ULN plus ALT and AST are \leq ULN plus alkaline phosphatase, hemoglobin, and reticulocyte count are all \leq ULN.

- Albumin \leq ULN;
- PT \leq ULN.

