Note: "Enrolled" means a participant's, or their legally authorized representative's, agreement to participate in a clinical study following completion of the informed consent process and assignment to study intervention. A participant will be considered enrolled if the informed consent is not withdrawn prior to participating in any study activity after screening. Potential participants who are screened for the purpose of determining eligibility for the study, but do not participate in the study, are not considered enrolled, unless otherwise specified by the protocol.

Study Population:

Key inclusion and exclusion criteria are listed below:

Key Inclusion Criteria

Participants must meet the following key inclusion criteria to be eligible for study enrollment:

All Groups

- Males or females between the ages of 18 (or the minimum country-specific age of consent if >18) and 75 years, inclusive at the screening visit.
- Willing and able to comply with all scheduled visits, treatment plan, laboratory tests, lifestyle considerations, and other study procedures.
- BMI of 17.5 to 38.0 kg/m², inclusive, and a total body weight >50 kg (110 lb).
- Capable of giving signed informed consent.

Additional for Group 1 Only (without HI)

- At screening, no clinically relevant abnormalities identified by a detailed medical history, complete physical examination, including BP and pulse rate measurement, standard 12-lead ECG and clinical laboratory tests.

- At screening, meet the demographic-matching criteria, including body weight within ± 15 kg and age within ± 10 years, of the average of the pooled hepatic impairment groups, as provided by the sponsor.
- No known or suspected hepatic impairment and meet all the following criteria based on screening laboratory tests: ALT \leq ULN, AST \leq ULN, T bili \leq ULN, albumin \leq ULN, and PT \leq ULN.

Additional for Groups 2-4 Only (Mild, Moderate, and Severe HI)

- Stable hepatic impairment that meets criteria for Class A, B, or C of the Child-Pugh classification with no clinically significant change in disease status within 28 days before screening.
- Stable concomitant medications for the management of individual participant's medical history.

Key Exclusion Criteria

Participants with any of the following characteristics/conditions will be excluded:

All Groups

- Any condition possibly affecting drug absorption (eg, prior bariatric surgery, gastrectomy, ileal resection).

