5.2.2. Additional Exclusion Criteria for Group 1 *Only* (without HI)

1. Evidence of chronic liver disease including history of hepatitis, hepatitis B, or hepatitis C or evidence of any of the following, as assessed by sponsor approved laboratory, with a single repeat, permitted to assess eligibility, if needed:
 - Hepatitis B virus, defined by presence of hepatitis B surface antigen (HBsAg);
NOTE: while *not* part of the tests assessed in this study, a previously positive hepatitis B surface antibody result due to vaccination is permissible.
 - Hepatitis C infection, defined by presence of HCVAb **and** HCV RNA.
2. History of alcohol abuse or binge drinking and/or any other illicit drug use or dependence within 6 months of screening. Binge drinking is defined as a pattern of 5 (male) and 4 (female) or more alcoholic drinks in about 2 hours. As a general rule, alcohol intake should not exceed 14 units per week (1 unit = 8 ounces (240 mL) beer, 1 ounce (30 mL) of 40% spirit or 3 ounces (90 mL) of wine).
3. Screening **supine** standard 12-lead ECG demonstrating QTcF interval >450 ms or a QRS interval >120 ms. If QTcF exceeds 450 ms, or QRS exceeds 120 ms, the ECG should be repeated 2 more times and the average of the 3 QTcF or QRS values should be used to determine the participant's eligibility.
4. Screening **seated** SBP \geq 140 mmHg or DBP \geq 90 mmHg, following \geq 5 minutes of seated rest. If SBP is \geq 140 mmHg or DBP \geq 90 mmHg, the BP assessment should be repeated 2 more times and the average of the 3 BP values should be used to determine eligibility.
5. Use of **chronic** prescription medications within 7 days or 5 half-lives (whichever is longer) prior to Day 1, or for prohibited medications, use within the required washout/restriction period provided in [Appendix 9](#).

NOTE: Use of selected, limited prescription and non-prescription medications may be permitted **on a case-by-case basis** after approval from the sponsor (refer to [Section 6.9](#) for details).

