10.10. Appendix 10: Child-Pugh Classification of Liver Dysfunction

Table 7. Scoring for Child-Pugh Classification¹⁰

| Group | | Child-Pugh Score | Level of Dysfunction | Total Score (tally based on assessment of parameters in Table 8) |
|-------|--|------------------|----------------------------|---|
| 1 | | Not Applicable | Without hepatic impairment | Not Applicable |
| 2 | | A | Mild | 5-6 |
| 3 | | B | Moderate | 7-9 |
| 4 | | C | Severe | ≥10 |

Table 8. Derivation of Child-Pugh Classification Score

| Assessment Parameters | Assigned score for observed findings | | |
|---|--------------------------------------|--------------|------------------------|
| | 1 point | 2 points | 3 points |
| Encephalopathy grade ^a (refer to Table 9 below) | 0 | 1 or 2 | 3 or 4 ^a |
| Ascites | Absent | Asymptomatic | Requiring intervention |
| Serum T bili, mg/dL | <2 | 2 to 3 | >3 |
| Serum albumin, g/dL | >3.5 | 2.8 to 3.5 | <2.8 |
| PT, sec prolonged | <4 | 4 to 6 | >6 |

a. Participants with a prior history of Grade 3 or 4 encephalopathy who are *currently* receiving an intervention [eg, lactulose or lactitol, alone or in combination with rifaximin, and/or neomycin] to manage encephalopathy related signs and symptoms should be scored for encephalopathy grading *based on their presentation while on intervention at the screening visit* and can be included in Study C5241012 as long as they do *not* have clinically active Grade 3 or 4 encephalopathy.

Table 9. Determination of Encephalopathy Grade

| Encephalopathy Grade | Definition |
|----------------------|---|
| 0 | Normal consciousness, personality, neurological exam |
| 1 | Restless, sleep disturbed, irritable/agitated, tremor, impaired handwriting |
| 2 | Lethargic, time-disoriented, inappropriate, asterixis, ataxia |
| 3 ^a | Somnolent, stuporous, place-disoriented, hyperactive reflexes, rigidity |
| 4 ^a | Unrousable coma, no personality/behavior, decerebrate |

a. Participants with clinically active Grade 3 or 4 encephalopathy are excluded.

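### The Group 1 albumin criterion is bounded on the wrong side: it rejects high values and lets every low value through

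*Protocol*

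**What the plan says.** Protocol 5.1 makes the inclusion criteria cumulative: "Participants are eligible to be included in the study only if all of the following criteria apply". For Group 1, section 5.1.2 item 3 begins "No known or suspected hepatic impairment, and meet all the following criteria at screening" and lists five laboratory limits: ALT, AST, T bili, albumin and PT, each at or below ULN, with one repeat allowed. The synopsis (section 1.1) introduces the same five upper limits with "No known or suspected hepatic impairment and meet all the following criteria based on screening laboratory tests". No section of the protocol or SAP sets a lower albumin limit for Group 1.

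Appendix 10, Table 8, has a row for "Serum albumin, g/dL" that gives 1 point above 3.5, 2 points from 2.8 to 3.5 and 3 points below 2.8. The row for "PT, sec prolonged" gives more points as PT lengthens.

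The Gilbert syndrome note in 5.1.2 uses the same upper-limit form: "alkaline phosphatase, hemoglobin, and reticulocyte count are all" to be at or below ULN.

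**The concern.** Five different tests carry the same inequality, although one of them signals impairment in the opposite direction from the rest. A limit meant to keep poor hepatic synthetic function out of the control group should exclude low albumin. This one excludes only high albumin, which Table 8 scores as best. Because section 5 does not permit waivers, a healthy volunteer whose albumin stays above ULN on repeat must be refused.

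The stake is the control group. Protocol 9.3.2.2 and SAP 6.1 compare mild, moderate and severe impairment each with Group 1. A control with unrecognised impairment would therefore affect every primary ratio at once. Protocol 9.3.2.3 itself names serum albumin as a possible hepatic function measure for the supplementary regression.

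**Working it through.** The plan has no figure of its own on this point, so the check sets the sections side by side and then bounds the possible effect.

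**Step 1. Direction of each limit** (5.1.2 item 3 against Table 8)

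| Test | Direction scored as worse in Table 8 | Group 1 limit | Agree? |
|---|---|---|---|
| T bili | Higher | Upper | Yes |
| PT | Longer | Upper | Yes |
| Albumin | Lower | Upper | No |

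ALT and AST are not in Table 8; Appendix 6 treats elevation as the sign of injury, so their upper limits are correctly directed.

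**Step 2. Can a low-albumin candidate pass all five numeric limits?** Take no encephalopathy, no ascites, T bili at or below ULN (assumed below 2 mg/dL, since the laboratory's ULN is not given) and PT at or below ULN (taken as less than 4 seconds prolonged). Each of these scores 1 point.

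- Albumin above 3.5 g/dL: 1+1+1+1+1 = 5.
- Albumin 2.8 to 3.5 g/dL: 2+1+1+1+1 = 6, Class A range.
- Albumin below 2.8 g/dL: 3+1+1+1+1 = 7, Class B range.

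All three candidates meet the five limits. A fully normal person already scores 5, which is also in the Class A range (5 to 6), so the 6-point case shows little. The 7-point case shows that the numeric limits alone would pass someone scoring in the moderate range. Child-Pugh does not define Group 1, so the tally shows only what the numeric limits let through.

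**Step 3. Effect on the ratios if such a control is enrolled.** The analysis compares group means of log exposure. If k of n controls have f times the exposure of the others, the Reference log mean rises by (k/n)·ln f, so each Test/Reference ratio is multiplied by f^(−k/n). The values of f and k are assumptions, with k = 1; n = 8 is planned and n = 10 is the maximum (Protocol 4.1, Table 3).

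| f | n = 8 | n = 10 |
|---|---|---|
| 1 | 1.00 | 1.00 |
| 1.25 | 0.972 | 0.978 |
| 1.5 | 0.951 | 0.960 |
| 2 | 0.917 | 0.933 |

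**Step 4. Against the planned precision.** The 100% row of Protocol Table 5 has an upper limit of 175.52, so the log half-width is ln(175.52/100) = 0.563. With n = 8 the shift is ln(1.25)/8 = 0.028 to ln(2)/8 = 0.087, and 0.028/0.563 = 5%, 0.087/0.563 = 15%.

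**Step 5. Direction.** For f above 1 the ratios fall, but whether that is toward or away from 1 depends on the true ratio. At f = 1.25, a true 1.50 becomes 1.50 × 0.972 = 1.459 (nearer 1), and a true 1.00 becomes 0.972 (further from 1).

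**The case against.** The strongest reply is that the protocol already covers this in substance. All criteria must hold together. Item 1 of 5.1.2 excludes clinically relevant abnormalities, including laboratory ones, and albumin is in the Table 6 panel. Item 3 itself rules out known or suspected impairment. ALT, AST, T bili and PT must all be at or below ULN, and PT is a correctly directed check on synthetic function. Section 5.2.2 item 1 excludes "Evidence of chronic liver disease including history of hepatitis, hepatitis B, or hepatitis C or evidence of any of the following", followed by hepatitis B and C markers. Exclusion 4 in 5.2.1 lets the investigator refuse anyone with an unsuitable laboratory abnormality. An albumin below 2.8 g/dL would be hard to pass under item 1.

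All of that stands, and it makes enrolment of an impaired control unlikely. It does not supply an albumin threshold, so in a multicentre study the decision on a low value is left to each site.

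The second reply is that the bias figures are assumed and f = 2 is generous. Section 4.2 mentions increases above 2-fold only for some compounds in severe impairment, and a human unbound fraction of 67% leaves limited room for albumin to act through binding alone. That also stands: the upper end of the range is a bound for illustration, not an expectation. Section 4.2 itself says "There is uncertainty of the effect of HI on PF-07923568 PK".

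**Conclusion.** The albumin limit is wrong as written, in both 5.1.2 item 3 and the synopsis. It does no screening in the direction that Table 8 treats as impairment, and it can reject a suitable control.

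The documents give neither the size nor the direction of any bias. It is nil if the other criteria catch every case. With one misclassified control in 8 and an assumed exposure of 1.25 to 2 times the others, all three ratios are multiplied by 0.972 to 0.917, at most about 15% of the Table 5 log half-width. The sample size and Table 5 do not change.

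The upper-only hemoglobin limit in the Gilbert note has the same form but is minor: it applies to Gilbert participants only, and the reticulocyte limit in that note already screens for haemolysis.

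**What to change.** In Protocol 5.1.2 item 3 and in the synopsis, require Group 1 albumin to be at or above LLN, or within the laboratory's reference range. The documents do not give the laboratory's LLN, so the sponsor should check how it sits against the 3.5 g/dL cut in Table 8. In the same amendment, hemoglobin in the Gilbert note can be given a lower bound at LLN, keeping the upper bounds on alkaline phosphatase and reticulocyte count; this part is optional.

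The cost is a short amendment, which needs IRB/EC approval before use (Protocol 10.1.1), and at most an occasional extra Group 1 screen failure. No new test is needed, since albumin and hemoglobin are in Table 6. Group 1 recruitment may start only when about 75% of Groups 2-4 have been dosed (Protocol 4.1), so the change can be made before it opens.
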